12.4.4. Sub-Group Analysis

Subgroup analyses for the primary outcomes will evaluate the treatment effect across the following subgroups:

- Patients enrolled vs. not enrolled/treated in other therapeutic clinical trials
- >= 60 years versus less than 60 years of age
- Sex
- Ethnicity
 - White/Black/Hispanic/Asian/Other
- Presence of medical co-morbidities
 - diabetes (yes/no)
 - o cardiac (yes/no)
 - respiratory (yes/no)
- Smoking History
 - Ever smoker/current smoker/never
 - 15 pack year history of smoking versus not
- Obesity (BMI >= 30 vs <30)
- Onset of symptoms > 12 days before randomization (including non-respiratory symptoms)
 versus not
- Timing of administration of CCP from diagnosis of COVID-19 (<=72 hours vs >72 hours)
- Severity of illness of donors (hospitalized vs not)
- ABO blood type of recipients (A vs other, B vs other, O vs other, AB vs other)
- CCP from one donor vs CCP from two donors
- Detectable vs non-detectable viral plasma viral load at baseline
- Anti-SARS-CoV-2 seropositivity at baseline
- Oxygen status at baseline (≤ 2L vs > 2L)

A forest plot will display confidence intervals across subgroups. Interaction tests will be conducted to determine whether the effect of treatment varies by subgroup.

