4.4.2. Standard of Care

Patients receiving standard of care will receive all medical care as per routine practices at each site.

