5.5. Packaging, Labeling and Storage

Labels bearing the ISBT 128 donation identification will be printed and placed on all collection bags and blood tubes before donation. After donation, plasma will be shipped to a component processing facility at Héma-Québec, Canadian Blood Services, or New York Blood Center and will be frozen at -18°C within 8-24 hours of collection. In Hemorio and in Magen David Adom National Blood Services the plasma will be collected at the same place where the component process facility is located. When results of regulatory analyses become available (this usually takes less than 48 hours) and the product can be released for transfusion, a new label will be applied on the plasma bag showing all product information including the ABO group. The plasma will also be labeled as "convalescent plasma" at Canadian, Brazilian, and Israeli sites and "apheresis plasma" at United States sites.

5.5.1. For Canadian Sites:

The sponsor shall ensure that the drug bears a label that sets out the following information in both official languages:

- (a) a statement indicating that the drug is an investigational drug to be used only by a qualified investigator;
- (b) the name, number or identifying mark of the drug;
- (c) the expiration date of the drug;
- (d) the recommended storage conditions for the drug;
- (e) the lot number of the drug;
- (f) the name and address of the sponsor;
- (g) the protocol code or identification.

A segregated storage area will be set up and used to keep CCP apart from the other plasma products. A product list will be kept up to date in order to know at all times the volume of CCP available for each ABO blood group. When requested for transfusion, the products will be shipped to the hospital through the regular transportation system for blood products or to pre-identified regional "hub" hospitals where inventory will be maintained. Large sites and those at a geographical distance of more than 200 km may be permitted to hold a stock of one 500 mL dose for each ABO blood group and smaller sites will only be shipped the investigation product once a patient has been randomized to the active treatment arm.

5.5.2. For United States Sites:

The sponsor shall ensure that the drug bears a label that sets out the following information in English:

- (a) A statement indicating that the drug is a new drug limited by federal (or United States) law for investigational use only;
- (b) The name, number or identifying mark of the drug;

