8.3. Collection of daily hospital data

Baseline data will be collected on Day 1 (see Section 8.5).

During the index hospital admission, daily data will be collected until discharge or Day 30 from randomization, whichever comes first. For enrolled patients who are still in hospital beyond Day 30, the date of discharge or death will be recorded up until Day 90 at which point data collection will be censored. This information will be obtained by reviewing the medical chart, by telephone follow-up or, if feasible through, provincial/state or national databases.

If the patient has routine blood drawn for laboratory testing pre-randomization and between 24 hours and 5 days (sample closest to 48 hours will be selected in preference) post-randomization, the discard plasma/serum from that sample will be retrieved, aliquoted and frozen for future testing. Alternatively, an extra tube can be added to the routine blood draw for research.

A Schedule of Assessment Events is available below for reference.

Schedule of Assessment Events

			Follow up		
Visit	Screening	Baseline (D1)	D2 - D30 ⁽¹⁾ (or until discharge)	D30 ⁽²⁾ (if patients discharged)	D90
Time Window (days)				+/- 3	+/- 7 days
Informed Consent/Assent	Х				
Verify Eligibility Criteria	X				
Randomization		Х			
CCP Administration (3)		Х			
Demographics		Х			
Co-morbidities		Х			
COVID-19 History ⁽⁴⁾		Х			
Height and Weight		Х			
Vital Signs		Х			
SpO ₂		Х	Х		
FiO ₂		Х	X		
COVID treatments		Х	Х	Х	
Hospitalization Daily Assessment (5)		Х	X		
Results of blood tests (done as per		Х	X ⁽⁶⁾		
clinical need)					
EQ-5D-5L ⁽⁷⁾		Х		Х	
Vital Status (dead/ alive)			Х	Х	X
Adverse Event Review		Х	Х	Х	
Discharge status (8)				Х	
Mechanical Ventilation since discharge				Х	
Viral load, cytokines and anti-CoV-2 titers ⁽⁹⁾		Χ	Х		

⁽¹⁾ Only collected if still hospitalized

⁽²⁾ Phone call if subject is already discharged from the hospital

⁽³⁾ Only for subject randomized to the convalescent plasma treatment

⁽⁴⁾ Includes date of first symptoms; description of symptoms, and date of diagnostic test

⁽⁵⁾ Mechanical ventilation, ECMO, renal replacement therapy or myocarditis

⁽⁶⁾ Daily from Day 1-7, then Day 14 +/- 3 days

⁽⁷⁾ EQ-5D-5L to be collected on Day 1 after consent and prior to CCP administration and on Day 30 regardless of hospitalization status

⁽⁸⁾ Discharge or hospital status (admitted, home, local hospital, longterm care facility)

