4.4. Sub-Group Analyses

Subgroup analyses will be carried out to assess whether the effect of treatment varies across subgroups defined according to the following criteria:

- Patients enrolled vs. not enrolled/treated in other therapeutic clinical trials
- ≥ 60 years versus less than 60 years of age
- Sex
- Ethnicity
 - White/Black/Hispanic/Asian/Other

- Presence of medical co-morbidities
 - diabetes (yes/no)
 - cardiac (yes/no)
 - respiratory (yes/no)
- Smoking History
 - Ever smoker/current smoker/never
 - 15 pack year history of smoking versus not
- Obesity (BMI ≥ 30 vs <30)
- Onset of symptoms > 12 days before randomization (including non-respiratory symptoms) versus not
- Timing of administration of CCP from diagnosis of COVID-19 (≤ 72 hours vs >72 hours)
- Severity of illness of donors (hospitalized vs not)
- ABO blood type of recipients (A vs other, B vs other, O vs other, AB vs other)
- Detectable vs non-detectable viral plasma viral load at baseline
- Anti-SARS-CoV-2 seropositivity at baseline
- Oxygen status at baseline ($\leq 2L$ vs $> 2L$)

These subgroup analyses will be carried out by estimating the treatment effect within subgroups and providing 95% confidence intervals and p-values.

In addition the effect of plasma from one donor will be compared to the effect of plasma from two donors.

Any additional exploratory sub-group analyses carried out will be based on regression models involving treatment, the subgroup variable and the respective interaction. The findings from such post-hoc analyses will be reported as hypothesis generating if the test of the null hypothesis that the interaction term is zero gives a statistically significant finding of heterogeneity of the effect.

4.5.Safety Reports for the IDSMC

Monthly reports on logistical issues, donor recruitment, and patient accrual overall and by study site will be provided to the IDSMC. Information on antibody test results will also be provided as available. These reports will also give tabulations of i. adverse events, ii. serious adverse events, and iii. CPP transfusion-related adverse events. If the IDSMC requests more or less frequent reports on this data, they will be provided. The reports will be created by an independent statistician who is unblinded to the treatment assignment.

4.6.Exploratory Analysis of the Role of anti-SARS-CoV-2 antibodies

4.6.1.Neutralizing antibodies

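### Timing of plasma, donor severity and number of donors have no value in the control arm, so they cannot serve as treatment-effect subgroups; Protocol and SAP also differ on number of donors

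*Protocol*

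**What the plan says.** Protocol 12.4.4 gives one list of subgroups for the primary outcome. Most are baseline factors such as age, sex and oxygen status. Three are not:

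- "Timing of administration of CCP from diagnosis of COVID-19 (<=72 hours vs >72 hours"
- donor severity (hospitalised or not)
- "CCP from one donor vs CCP from two donors"

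For the whole list the Protocol plans a forest plot, and "Interaction tests will be conducted to determine whether the effect of treatment varies by subgroup".

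SAP 4.4 is close but not identical. It keeps timing of CCP and "Severity of illness of donors (hospitalized vs not" in its list, with an effect estimate, 95% interval and p-value in each subgroup. Number of donors leaves the list for a sentence of its own: "In addition the effect of plasma from one donor will be compared to the effect of plasma from two donors". No method follows. The SAP section mentions no forest plot, and it names interaction models only for additional exploratory subgroups.

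On who has these data, the Protocol's schedule of assessments (8.3) marks CCP administration "Only for subject randomized to the convalescent plasma treatment". For the other arm, Protocol 4.4.2 says "Patients receiving standard of care will receive all medical care as per routine practices at each site". On Canadian supply, Protocol 5.5 adds that "smaller sites will only be shipped the investigation product once a patient has been randomized to the active treatment arm".

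**The concern.** A subgroup treatment effect compares randomised arms among patients who share a characteristic. That requires the characteristic to be defined in both arms, preferably before randomisation. A standard-of-care patient has no infusion time, no donor and no donor count, and neither document says how to assign one. At smaller Canadian sites not even a reserved unit exists, because the product is shipped only after allocation to CCP. A patient allocated to CCP but never transfused has no value either, so these analyses also leave the intention-to-treat set of SAP 3.1.

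Rows for these variables would stand in the forest plot beside valid subgroups and be read as effect modification. What they show could equally come from blood supplier, centre, calendar time or patient prognosis. A wrong reading could affect which plasma is thought to work.

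**Working it through.** **Plan's own figure.** The plan gives no figure for these subgroups. The sample size supplies the inputs: control risk 30%, CCP risk 0.75 × 30% = 22.5%, 400 control and 800 CCP patients, two-sided 0.05 (Protocol 12.1).

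- Average risk = (400 × 0.30 + 800 × 0.225)/1200 = 0.25.
- Null SE = √[0.25 × 0.75 × (1/400 + 1/800)] = 0.0265.
- Alternative SE = √(0.21/400 + 0.1744/800) = 0.0273.
- Power = Φ[(0.075 − 1.96 × 0.0265)/0.0273] = 80.1%. The stated 80% reproduces.

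**Step 1: is the interaction identified?** Let X = 1 for CCP, and let S be the subgroup variable, observed only when X = 1. The usual model has columns 1, X, S and XS.

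- Controls coded S = 0: S equals XS in every patient.
- Controls coded S = 1: S equals 1 − X + XS in every patient.

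Either way one column is redundant. A numerical check gives rank 3 of 4 for both codings. With S defined at baseline in both arms the rank is 4.

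**Step 2: what does setting each CCP subset against controls estimate?** With subset risks pA and pB and a common control risk pC, the ratio of relative risks is (pA/pC)/(pB/pC) = pA/pB. For assumed pA = 20% and pB = 25%:

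- pC = 20%: RRs 1.00 and 1.25, ratio 0.80
- pC = 30%: RRs 0.67 and 0.83, ratio 0.80
- pC = 40%: RRs 0.50 and 0.625, ratio 0.80

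The control arm cancels. The contrast is CCP patients against other CCP patients, and randomisation does not protect it.

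**Step 3: how large could the artefact be?** All subset risks here are assumptions; the documents give none. Assume CCP has no effect, overall risk is 30%, the 800 CCP patients split 400/400, and an unadjusted pooled control arm is used.

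- 27% v 33%: 0.27/0.30 = 0.90 and 0.33/0.30 = 1.10. A two-sided 0.05 test between the subsets is significant in about 46% of trials.
- 25% v 35%: 0.25/0.30 = 0.83 and 0.35/0.30 = 1.17; about 87%.

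More generally, let r be the prognostic relative risk between the subsets and f the share of CCP patients in the higher-risk one. Then pA = 0.30/(f·r + 1 − f) and pB = r·pA.

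- f = 0.5, r = 1.25: 26.7% v 33.3%, RRs 0.89 and 1.11, significant in 54%.
- f = 0.5, r = 1.5: 24% v 36%, RRs 0.80 and 1.20, significant in 96%.
- f = 0.2, same r values: significant in 43% and 91%.

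**Step 4: how far is timing affected by surviving to transfusion?** Protocol 4.2 and 5.7 require infusion within 24 hours of randomisation. In compliant patients, time from diagnosis to CCP exceeds time from diagnosis to randomisation by at most 24 h. Only patients randomised between 72 − 24 = 48 h and 72 h after diagnosis can change category.

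**Step 5: what would a baseline timing subgroup deliver?** The diagnostic test date is collected at baseline (Protocol 8.3 schedule, footnote 4; 8.4). The interaction is then a randomised contrast. On the log relative risk scale, the variance is the sum of (1 − p)/(np) over the four cells. For an assumed 50:50 split and RRs of 0.6 v 0.9, the SE is 0.204, and power is Φ(0.405/0.204 − 1.96) = 51%. With a 30:70 split, the smaller group having the stronger effect, it is 43%. For RRs of 0.75 v 1.0 it is 32% and 27%.

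**The case against.** The case for the plan has real substance.

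- **The SAP has moved part of the way.** It no longer lists number of donors as a subgroup with its own effect against control. A reader might infer that both documents plan all three variables with forest plots and interaction tests. They do not: for the listed subgroups, those two displays appear only in the Protocol.
- **Controls need not be pooled.** A reader might infer that the whole control arm is the only possible comparator. Randomisation is stratified by centre (Protocol 4.3). Supplier is a single organisation in the United States, Brazil and Israel, and one of two in Canada (Protocol 5.4). Controls therefore exist within centre and largely within supplier. If the 25% and 35% risks come from suppliers, supplier-matched controls give 25/25 and 35/35, both 1.00. This stands against the size of the illustration. It does not rescue the contrast: within a stratum holding both subsets the control risk cancels again, and calendar time and patient prognosis remain.
- **Timing is a near miss.** A reader might infer a serious survival-to-transfusion bias. The 24-hour rule makes that window short. The main defect is the missing control value.
- **The structure is recognised elsewhere.** For plasma titres, SAP 4.6.1 and supplement 2.2 fit a treatment-by-marker term without a marker main effect, and SAP 4.6.1 says so. That coefficient is estimable, though not randomised. Supplement section 2 adjusts marker analyses for provider, supplement 2.1 plans regressions within the CCP arm, and Protocol 12.4.5 treats donor characteristics as exploratory. None of this is extended to the three variables here, so the gap stands, but most of the remedy is already written.

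**Conclusion.** The point holds in a limited form. In Protocol 12.4.4 for all three variables, and in SAP 4.4 for timing and donor severity, the plan promises treatment effects in subgroups that do not exist in the control arm. An interaction with a subgroup main effect is not identified. Any comparison that can be computed is a non-randomised contrast within the CCP arm. For number of donors, the remaining faults are a difference between the documents, no stated method and no non-randomised label.

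The relative risks of 0.83 and 1.17, or 0.90 and 1.10, should not be read as the expected distortion. They require an unadjusted pooled control arm, assumed risks, complete separation of suppliers between the subsets, and an equal split. The documents establish none of these. They show that confounding of a plausible size could look like effect modification.

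These are subgroup analyses; the primary test is unaffected. The text should be changed because it cannot be carried out as a randomised comparison and the correction is cheap.

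**What to change.** Make the same changes in Protocol 12.4.4 and SAP 4.4.

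1. **Timing.** Redefine the subgroup as time from COVID-19 diagnostic test to randomisation, at most 72 h against more than 72 h. State the cut in days if only dates are recorded. Patients in both arms then have a value.
2. **Donor severity and number of donors.** Remove both from the subgroup, forest-plot and interaction lists. Place them with the exploratory analyses (Protocol 12.4.5, SAP 4.6) as associations within the CCP arm. Adjust for supplier, as supplement section 2 does for markers, and for age and baseline oxygen. Label them non-randomised.
3. **Donor severity data.** Protocol 8.1 names severity for Canadian and Brazilian sites but not for US and Israeli sites, although both lists are only examples. Restrict the analysis to suppliers that report severity, and state how two donors of differing severity are classed.
4. **Method for one v two donors.** State the model, so that Protocol and SAP agree. If a supplier provides only one format, its patients add nothing to the adjusted comparison, and the report should say so.

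The cost is wording; no new data are needed. The downside is that donor factors are no longer reported as treatment-effect subgroups. The repaired timing interaction would have modest power, 27% to 51% in the scenarios assumed above, so a null result there should not be read as absence of effect modification.

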12.4.5. Exploratory Analysis

Association between anti-SARS-CoV2 antibody in CCP and the primary outcome of intubation or death will be assessed using logistic regression. Anti-SARS-CoV-2 antibodies will be characterized according to the amount of antibodies against the native spike protein and the RBD, as well as to their neutralizing and Fc functions. Exploratory analyses will also examine possible associations between donor characteristics and treatment efficacy. Change in viral load and in anti-SARS-CoV2 serology in the recipient following transfusion will also be assessed and correlated with treatment outcome.

APPENDIX 1: Declaration of Helsinki

WMA DECLARATION OF HELSINKI ETHICAL PRINCIPLES FOR MEDICAL RESEARCH INVOLVING HUMAN SUBJECTS

Adopted by the 18th WMA General Assembly, Helsinki, Finland, June 1964 and amended by the:

29th WMA General Assembly, Tokyo, Japan, October 1975
35th WMA General Assembly, Venice, Italy, October 1983
41st WMA General Assembly, Hong Kong, September 1989
48th WMA General Assembly, Somerset West, Republic of South Africa, October 1996
52nd WMA General Assembly, Edinburgh, Scotland, October 2000
53rd WMA General Assembly, Washington DC, USA, October 2002 (Note of Clarification added)
55th WMA General Assembly, Tokyo, Japan, October 2004 (Note of Clarification added)
59th WMA General Assembly, Seoul, Republic of Korea, October 2008
64th WMA General Assembly, Fortaleza, Brazil, October 2013

Preamble

1. The World Medical Association (WMA) has developed the Declaration of Helsinki as a statement of ethical principles for medical research involving human subjects, including research on identifiable human material and data.

The Declaration is intended to be read as a whole and each of its constituent paragraphs should be applied with consideration of all other relevant paragraphs.

2. Consistent with the mandate of the WMA, the Declaration is addressed primarily to physicians. The WMA encourages others who are involved in medical research involving human subjects to adopt these principles.

General Principles

- 3. The Declaration of Geneva of the WMA binds the physician with the words, "The health of my patient will be my first consideration," and the International Code of Medical Ethics declares that, "A physician shall act in the patient's best interest when providing medical care."
- 4. It is the duty of the physician to promote and safeguard the health, well-being and rights of patients, including those who are involved in medical research. The physician's knowledge and conscience are dedicated to the fulfilment of this duty.
- 5. Medical progress is based on research that ultimately must include studies involving human subjects.
- 6. The primary purpose of medical research involving human subjects is to understand the causes, development and effects of diseases and improve preventive, diagnostic and therapeutic interventions (methods, procedures and treatments). Even the best proven interventions must be evaluated continually through research for their safety, effectiveness, efficiency, accessibility and quality.
- 7. Medical research is subject to ethical standards that promote and ensure respect for all human subjects and protect their health and rights.
- 8. While the primary purpose of medical research is to generate new knowledge, this goal can never take precedence over the rights and interests of individual research subjects.

- 9. It is the duty of physicians who are involved in medical research to protect the life, health, dignity, integrity, right to self-determination, privacy, and confidentiality of personal information of research subjects. The responsibility for the protection of research subjects must always rest with the physician or other health care professionals and never with the research subjects, even though they have given consent.
- 10. Physicians must consider the ethical, legal and regulatory norms and standards for research involving human subjects in their own countries as well as applicable international norms and standards. No national or international ethical, legal or regulatory requirement should reduce or eliminate any of the protections for research subjects set forth in this Declaration.
- 11. Medical research should be conducted in a manner that minimizes possible harm to the environment.
- 12. Medical research involving human subjects must be conducted only by individuals with the appropriate ethics and scientific education, training and qualifications. Research on patients or healthy volunteers requires the supervision of a competent and appropriately qualified physician or other health care professional.
- 13. Groups that are underrepresented in medical research should be provided appropriate access to participation in research.
- 14. Physicians who combine medical research with medical care should involve their patients in research only to the extent that this is justified by its potential preventive, diagnostic or therapeutic value and if the physician has good reason to believe that participation in the research study will not adversely affect the health of the patients who serve as research subjects.
- 15. Appropriate compensation and treatment for subjects who are harmed as a result of participating in research must be ensured.

Risks, Burdens and Benefits

16. In medical practice and in medical research, most interventions involve risks and burdens.

Medical research involving human subjects may only be conducted if the importance of the objective outweighs the risks and burdens to the research subjects.

17.All medical research involving human subjects must be preceded by careful assessment of predictable risks and burdens to the individuals and groups involved in the research in comparison with foreseeable benefits to them and to other individuals or groups affected by the condition under investigation.

Measures to minimize the risks must be implemented. The risks must be continuously monitored, assessed and documented by the researcher.

18. Physicians may not be involved in a research study involving human subjects unless they are confident that the risks have been adequately assessed and can be satisfactorily managed.

When the risks are found to outweigh the potential benefits or when there is conclusive proof of definitive outcomes, physicians must assess whether to continue, modify or immediately stop the study.

Vulnerable Groups and Individuals

19. Some groups and individuals are particularly vulnerable and may have an increased likelihood of being wronged or of incurring additional harm.

All vulnerable groups and individuals should receive specifically considered protection.

20. Medical research with a vulnerable group is only justified if the research is responsive to the health needs or priorities of this group and the research cannot be carried out in a non-vulnerable group. In addition, this group should stand to benefit from the knowledge, practices or interventions that result from the research.

Scientific Requirements and Research Protocols

- 21. Medical research involving human subjects must conform to generally accepted scientific principles, be based on a thorough knowledge of the scientific literature, other relevant sources of information, and adequate laboratory and, as appropriate, animal experimentation. The welfare of animals used for research must be respected.
- 22. The design and performance of each research study involving human subjects must be clearly described and justified in a research protocol.

The protocol should contain a statement of the ethical considerations involved and should indicate how the principles in this Declaration have been addressed. The protocol should include information regarding funding, sponsors, institutional affiliations, potential conflicts of interest, incentives for subjects and information regarding provisions for treating and/or compensating subjects who are harmed as a consequence of participation in the research study.

In clinical trials, the protocol must also describe appropriate arrangements for post-trial provisions.

Research Ethics Committees

23. The research protocol must be submitted for consideration, comment, guidance and approval to the concerned research ethics committee before the study begins. This committee must be transparent in its functioning, must be independent of the researcher, the sponsor and any other undue influence and must be duly qualified. It must take into consideration the laws and regulations of the country or countries in which the research is to be performed as well as applicable international norms and standards, but these must not be allowed to reduce or eliminate any of the protections for research subjects set forth in this Declaration.

The committee must have the right to monitor ongoing studies. The researcher must provide monitoring information to the committee, especially information about any serious AEs. No amendment to the protocol may be made without consideration and approval by the committee. After the end of the study, the researchers must submit a final report to the committee containing a summary of the study's findings and conclusions.

Privacy and Confidentiality

24. Every precaution must be taken to protect the privacy of research subjects and the confidentiality of their personal information.

Informed Consent

25. Participation by individuals capable of giving informed consent as subjects in medical research must be voluntary. Although it may be appropriate to consult family members or community leaders, no individual capable of giving informed consent may be enrolled in a research study unless he or she freely agrees.

26.In medical research involving human subjects capable of giving informed consent, each potential subject must be adequately informed of the aims, methods, sources of funding, any possible conflicts of interest, institutional affiliations of the researcher, the anticipated benefits and potential risks of the study and the discomfort it may entail, post-study provisions and any other relevant aspects of the study. The potential subject must be informed of the right to refuse to participate in the study or to withdraw consent to participate at any time without reprisal. Special attention should be given to the specific information needs of individual potential subjects as well as to the methods used to deliver the information.

After ensuring that the potential subject has understood the information, the physician or another appropriately qualified individual must then seek the potential subject's freely-given informed consent, preferably in writing. If the consent cannot be expressed in writing, the non-written consent must be formally documented and witnessed.

All medical research subjects should be given the option of being informed about the general outcome and results of the study.

- 27. When seeking informed consent for participation in a research study the physician must be particularly cautious if the potential subject is in a dependent relationship with the physician or may consent under duress. In such situations the informed consent must be sought by an appropriately qualified individual who is completely independent of this relationship.
- 28. For a potential research subject who is incapable of giving informed consent, the physician must seek informed consent from the legally authorized representative. These individuals must not be included in a research study that has no likelihood of benefit for them unless it is intended to promote the health of the group represented by the potential subject, the research cannot instead be performed with persons capable of providing informed consent, and the research entails only minimal risk and minimal burden.
- 29. When a potential research subject who is deemed incapable of giving informed consent is able to give assent to decisions about participation in research, the physician must seek that assent in addition to the consent of the legally authorized representative. The potential subject's dissent should be respected.
- 30. Research involving subjects who are physically or mentally incapable of giving consent, for example, unconscious patients, may be done only if the physical or mental condition that prevents giving informed consent is a necessary characteristic of the research group. In such circumstances the physician must seek informed consent from the legally authorized representative. If no such representative is available and if the research cannot be delayed, the study may proceed without informed consent provided that the specific reasons for involving subjects with a condition that renders them unable to give informed consent have been stated in the research protocol and the study has been approved by a research ethics committee. Consent to remain in the research must be obtained as soon as possible from the subject or a legally authorized representative.
- 31. The physician must fully inform the patient which aspects of their care are related to the research. The refusal of a patient to participate in a study or the patient's decision to withdraw from the study must never adversely affect the patient-physician relationship.
- 32. For medical research using identifiable human material or data, such as research on material or data contained in biobanks or similar repositories, physicians must seek informed consent for its collection, storage and/or reuse. There may be exceptional situations where consent would be impossible or

impracticable to obtain for such research. In such situations the research may be done only after consideration and approval of a research ethics committee.

Use of Placebo

33. The benefits, risks, burdens and effectiveness of a new intervention must be tested against those of the best proven intervention(s), except in the following circumstances:

Where no proven intervention exists, the use of placebo, or no intervention, is acceptable; or

Where for compelling and scientifically sound methodological reasons the use of any intervention less effective than the best proven one, the use of placebo, or no intervention is necessary to determine the efficacy or safety of an intervention and the patients who receive any intervention less effective than the best proven one, placebo, or no intervention will not be subject to additional risks of serious or irreversible harm as a result of not receiving the best proven intervention.

Extreme care must be taken to avoid abuse of this option.

Post-Trial Provisions

34.In advance of a clinical trial, sponsors, researchers and host country governments should make provisions for post-trial access for all participants who still need an intervention identified as beneficial in the trial. This information must also be disclosed to participants during the informed consent process.

Research Registration and Publication and Dissemination of Results

- 35. Every research study involving human subjects must be registered in a publicly accessible database before recruitment of the first subject.
- 36. Researchers, authors, sponsors, editors and publishers all have ethical obligations with regard to the publication and dissemination of the results of research. Researchers have a duty to make publicly available the results of their research on human subjects and are accountable for the completeness and accuracy of their reports. All parties should adhere to accepted guidelines for ethical reporting. Negative and inconclusive as well as positive results must be published or otherwise made publicly available. Sources of funding, institutional affiliations and conflicts of interest must be declared in the publication. Reports of research not in accordance with the principles of this Declaration should not be accepted for publication.

Unproven Interventions in Clinical Practice

In the treatment of an individual patient, where proven interventions do not exist, or other known interventions have been ineffective, the physician, after seeking expert advice, with informed consent from the patient or a legally authorized representative, may use an unproven intervention if in the physician's judgement it offers hope of saving life, re-establishing health or alleviating suffering. This intervention should subsequently be made the object of research, designed to evaluate its safety and efficacy. In all cases, new information must be recorded and, where appropriate, made publicly available.

